The information intervention may impact on this outcome through multiple mechanisms. Individuals who are made aware that the CVD risk for individuals with their risk factor profile is higher than they had anticipated, who are provoked to recognize that they face a non-negligible risk without having given serious thought to this risk previously and who are told by how much the risk could be reduced by quitting smoking, reducing blood pressure, losing weight etc, may be provoked to take actions to reduce their risk. Actions could include: going for a checkup at a RHU/CHC or other health facility with the possibility of subsequently being put on medication for hypertension, diabetes or high cholesterol, attempting to lose weight through diet and/or exercise, and quitting smoking. Any efforts that are

effective in reducing blood pressure, reducing weight and stopping smoking will translate into a reduced 10-year CVD risk score.

The lottery intervention may impact on the predicted 10-year CVD risk by inducing respondents to attend a RHU/CHC where they can access PhilPEN risk assessment. Given the age criterion for inclusion in the study (40+), according to the protocol all those attending a RHU/CHC should be subject to PhilPEN risk screening, which includes tests for blood glucose, urine protein and cholesterol, in addition to measures of blood pressure and weight taken in risk assessment. All those screened should be given counselling on smoking cessation, diet and exercise. Those with sufficiently high risk, should be given medication for hypertension and/or diabetes, which are supplied to RHU/CHCs by the department of health. According to the protocol, those with sufficiently high risk should also be given statins, although these are not supplied by the department of health.

The proportion of the population with elevated CVD risk is likely to be more important for population health than is the mean risk. Unfortunately, we do not have data that allow us to estimate the proportion with elevated risk predicted by the Globorisk algorithm. Hence, we cannot conduct power calculations for this outcome. However, we intend to estimate the impact on it providing that an ex-post calculation confirms that there is sufficient power. We will estimate effects on:

ii) Proportion with 10-year CVD risk (Globorisk prediction) $\geq \tau\%$

The threshold (τ) for elevated CVD risk will be set at 10%, and if there proves to be sufficient power, also 20% and 30%.

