Besides medication, blood pressure may be brought under control through changes in lifestyle, which our lottery intervention may impact on indirectly through the counselling that is part of the PhilPEN protocol and the information intervention may influence by revealing why an individual's risk is elevated. Besides smoking, we will test for effects on *alcohol consumption, diet (intake of fruit, vegetables and salty foods) and exercise*. Since we do not have base rate estimates of the means of these outcomes in the absence of any intervention, tests for effects on them will be subject to an ex-post power calculations confirming that there is sufficient power to detect effects.

Knowledge of CVD risk factors

Our information intervention will directly inform of CVD risk factors by explaining the reasons an individual's predicted risk is above the lowest level that would be attainable if risk factors were at their minimum levels. Contact with the PhilPEN primary prevention program may directly improve knowledge of CVD risk factors through counselling on healthy lifestyle. It is possible, therefore, that both interventions may improve knowledge of the causes of CVD. We will test for effects on an index of knowledge constructed from a battery of questions about CVD risk factors. Since we have no estimate of the mean of this score in the control group, we will conduct ex-post power analysis to establish whether there is indeed sufficient power to detect an effect on this score.

Outcomes specific to lottery intervention

For the lottery intervention, we will examine whether attending a RHU/CHC for a checkup increases the probability of receiving medical advice on the adoption of healthier habits, as is prescribed by the PhilPEN protocol. Specifically, we will estimate effects on:

- xii) The proportion of smokers/ex-smokers who have been advised by a doctor or health worker to quit smoking.
- xiii) The proportion of smokers/ex-smokers who have received counselling on smoking cessation.
- xiv) The proportion who have been advised by a doctor or other health worker to drink less alcohol (out of all who have ever consumed alcohol).
- xv) The proportion who have been advised by a doctor or other health worker to eat less salty and/or fatty food.
- xvi) The proportion who have been advised by a doctor or other health worker to eat more fruit & vegetables and/or grains & pulses.

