- xvii) The proportion who have been advised by a doctor or other health worker be more physically active.
- xviii) The proportion of individuals overweight or obese (at baseline) who have been encouraged by a health professional to lose weight.

Since we do not have estimates of base rates for these outcomes that can be used to conduct power calculations, estimating effects on them will be contingent on ex-post analyses establishing that there is sufficient power. In addition, we will monitor whether those who attend a RHU/CHC receive advice

(/counselling) on smoking, alcohol consumption, diet and exercise, as well as being tested for hypertension, diabetes and hyperlipidemia, and whether they receive the respective medications.

Outcomes specific to information intervention

The information intervention will be used to estimate effects on beliefs about the risk of CVD. Specifically, we will estimate the effect of providing information on:

- xix) the CVD base rate on mean perceived 10-year risk of heart attack or stroke for someone of same age and sex;
- xx) the predicted CVD risk for someone with same risk profile as the respondent on mean perceived own 10-year risk of heart attack or stroke (posterior CVD risk);
- xxi) the predicted CVD risk for someone with the respondent's age and sex but the optimal risk profile on the mean perceived own 10-year risk of heart attack or stroke if were to adopt healthy lifestyle.

We do not have information necessary conduct power calculations for outcomes xix)-xxi) and so will carry out ex-post analysis to establish whether we have sufficient power to test for effects on these outcomes.

Outcomes not specific to CVD

If either of the intervention were to be successful in reducing exposure to CVD risk factors, then, in the long term, health gains will arise from it. Over a 6-7 month follow-up period, we do not anticipate that there will be sufficient time for general health affects to materialize and be apparent in a sample of the size studied. Nonetheless, we will measure general health using the SF-36v1. We will also measure labour outcomes (employment, hours and earnings), although we do not anticipate that the follow-up duration and sample size will be sufficient to detect any effects that may exist. Analyses of these outcomes will only be undertaken if an ex-post power calculation confirms that there is sufficient power, although this will not address the issue of the length of the follow-up.

8. Sampling

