10.1 Parameter values

To the extent that it is possible given the estimates available, we have strived to base the choice of parameter values on evidence. However, it must be acknowledged that, as is often the case with power calculations, the evidence is often lacking or meagre, and we often must resort to guesstimates. In doing so, we have endeavoured to err on the side of conservatism and have conducted sensitivity analyses.

Power

Power is set to 80% and statistical significance to 5%.

Minimum detectable effect size

We calculate the sample size necessary to detect a small effect size (δ) defined as 0.2 standard deviation (SD) units (Cohen 1992). Consider our main outcome i) – the 10-year risk of a heart attack or stroke predicted by the office-based Globorisk algorithim. Given an estimated mean 10-year CVD risk of 11.35% in the control group, which we obtain from Globorisk for individuals aged 40-69 with mean values of all risk factors, if the standard deviation is one fifth of the mean, then an effect size of 0.2 SD corresponds to a 4% reduction in the mean. The assumption that the standard deviation is one fifth of the mean is based on estimates of the distribution of 10-year CVD risk scores (Gale et al 2014; Gray et al 2014). However, we caution that these estimates are not obtained using the Globorisk algorithm and most are for samples of high-income country populations.⁷

We deliberately choose a small effect size in order to ensure that our samples will be sufficient to detect only marginal impacts of the interventions on the risk factors that determine the CVD risk prediction. The logic is threefold. First, risk factors such as smoking and weight are notoriously hard to influence. Second, our information intervention is of unknown effectiveness and we recognize a possibility that a non-negligible fraction of respondents are unable to absorb the information provided on their CVD risks. Third, while the procedures defined by the PhilPEN protocol are proven to be effective, our aim is to establish effectiveness as the program is implemented, which may fall well short of the stipulated testing, medication and counselling.

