For mean systolic blood pressure (outcome iii), mean BMI (v) and mean waist circumference (viii), we obtain the estimated control group means from measures taken in the 2013 National Nutrition Survey (NNS) for individuals aged 40-69 (FNRI-DOST, 2015). The standard deviation is assumed to be one seventh of the mean for systolic blood pressure, one fifth of the mean for BMI and one ninth of the mean for waist circumference based on Ezzati et al (2004). In each case, we set the minimal detectable effect size to 0.2 SD units of the mean.

Control group proportions for elevated blood pressure (outcome iv), overweight/obese (vi), smoking (vii), central adiposity (ix), undiagnosed hypertension (x) and hypertension medication (xi) are also taken from the 2013 NNS for individuals aged 40-69. For these binary outcomes, we set the minimal detectable effect size to the small value defined by Cohen (1992) as 0.2 of his h-index.

Intra cluster correlation

⁷ Using the Framingham algorithm for 10-year CVD risk (D'Agostino et al 2008), Gale et al (2014) report a mean of 14.3% and a standard deviation of 2.59 for an English sample of 60+, non-frail persons with no history of CVD. A small study of 40+ employees without previous CVD in a region of Wales reports means (standard deviations) of non-laboratory based Framingham 10-year CVD risk of 10.7% (2.4) for males and 4.8% (1.2) for females (Gray et al 2014).

To the best of our knowledge, there are no estimates available of the intra cluster correlation for (predicted) 10-year CVD risk with clusters defined by communities resembling the size of Filipino barangays. Some idea of the correlation is given by ICCs for CVD risk factors, which determine predicted risk. Table 3 provides estimates of such ICCs for clusters defined at the level of primary care practice obtained from three North American studies.

While homogeneity of CVD risk factors within Filipino barangays need not necessarily closely resemble the homogeneity observed within primary care practices in North America, these estimates at least give an idea of the ICC that might be expected. We set the ICC at 0.1, which is almost twice the highest estimate for any risk factor in Table 3. This is even more conservative than might appear at first sight since one would expect there to be even less within community homogeneity in CVD risk predicted on the basis of all risk factors than there is in each individual risk factor individually.

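### Section 7 makes estimation of about half the listed outcomes depend on a later power check whose target effect is not stated, so randomised estimates can be withheld from data already collected

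*Combined protocol and SAP*

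**What the plan says.** Four statements in section 7 (Outcomes) make analysis depend on a later power result:

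- Outcome ii, the proportion above a CVD risk threshold: "we intend to estimate the impact on it providing that an ex-post calculation confirms that there is sufficient power". The threshold "for elevated CVD risk will be set at 10%, and if there proves to be sufficient power, also 20% and 30" per cent.
- Alcohol, diet and exercise: "tests for effects on them will be subject to an ex-post power calculations confirming that there is sufficient power to detect effects".
- Outcomes xii-xviii, advice and counselling received: "estimating effects on them will be contingent on ex-post analyses establishing that there is sufficient power".
- SF-36 and employment, hours and earnings: "Analyses of these outcomes will only be undertaken if an ex-post power calculation confirms that there is sufficient power".

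Two further statements are softer. For the knowledge index and for outcomes xix-xxi the plan announces a check but does not say that estimation depends on it; for xix-xxi the words are "so will carry out ex-post analysis to establish whether we have sufficient power to test for effects on these outcomes".

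Section 10.1 gives general settings: "Power is set to 80% and statistical significance to 5" per cent, an ICC of 0.1 and an autocorrelation of 0.6, the last two stated to apply to all outcomes in the main calculation. The small-effect target for binary outcomes (Cohen's h of 0.2) is tied to a named list: "Control group proportions for elevated blood pressure (outcome iv), overweight/obese (vi), smoking (vii), central adiposity (ix), undiagnosed hypertension (x) and hypertension medication (xi"). None of the outcomes on that list is conditional in section 7.

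**The concern.** A power condition on estimation means that an outcome can be measured in every arm and still have no effect estimate reported. Low power is a reason to show a wide interval. It is not a reason to leave the estimate out.

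Two groups of outcomes make this matter. The plan itself rates the proportion at elevated risk (outcome ii) as probably of greater consequence for population health than the average risk. Outcomes xii-xviii are the randomised evidence on whether a checkup leads to the advice that PhilPEN prescribes, which bears directly on the second study objective. Section 7 also promises to monitor, without any condition, what attenders receive. That is descriptive and does not replace a comparison that uses the randomisation.

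The usual reason given is that base rates are unknown. For outcome ii, the behaviours, knowledge, SF-36 and labour, that gap closes before follow-up: section 11 lists baseline modules on these topics and baseline measurement of the Globorisk inputs.

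**Working it through.** **Count.** Numbered outcomes i-xxi (21), plus alcohol, diet and exercise (3), the knowledge index (1), SF-36 (1) and three labour items (3), make 29. Explicitly conditional: outcome ii (1) + behaviours (3) + xii-xviii (7) + SF-36 (1) + labour (3) = 15, or 52%. If the 10% threshold is unconditional, 15 - 1 = 14. With labour as one item the count is 13 of 27. With the softer wording included it is 15 + 4 = 19 of 29.

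**Reproducing the plan's sample size.** Inputs are from section 10.1, with two-sided 5% assumed. For mean CVD risk, the difference is 11.35 - 10.89 = 0.46 and the SD is 11.35/5 = 2.27.

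- Unclustered n per arm = 2 × (2.27 × 2.80/0.46)² ≈ 382.
- Times the design effect 1 + 9 × 0.1 = 1.9 and the ANCOVA factor 1 - 0.6² = 0.64 ≈ 465, rounded up to 470 (whole clusters of 10).
- Divided by 0.6² for compliance = 1,306, as in Table 6.

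For an effect of 0.2 the same steps give 1,333, against 1,361 in Table 6 for binary outcomes (2% apart). The formula is close enough to use at the planned 1,361 per arm.

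**Power of the later check, if section 10 is carried over.** SE² = (2/n) × [1 + (m - 1) × ICC] × (1 - r²); power = Φ(effect × compliance/SE - 1.96). The effect is in SD or h units among those induced to attend.

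For outcomes asked of all respondents, n = 1,361 and m = 10. For xviii (overweight at baseline), n and m are multiplied by 0.31, giving n ≈ 422 and m = 3.1. The 31% is Table 5's control proportion with BMI above 25. It comes from a national survey of ages 40-69 before the trial's exclusions, so it is an assumption here.

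| Scenario (ICC, r, compliance) | All, 0.2 | xviii, 0.2 | xviii, 0.3 | xviii, 0.4 |
|---|---|---|---|---|
| 1 (0.1, 0.6, 0.6) | 81% | 51% | 84% | 98% |
| 2 (0.05, 0.6, 0.6) | 90% | 55% | 88% | 99% |
| 3 (0.1, 0.6, 0.5) | 66% | 38% | 70% | 91% |
| 4 (0.05, 0.6, 0.5) | 77% | 41% | 74% | 93% |
| 5 (0.1, 0.4, 0.6) | 70% | 41% | 74% | 93% |

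Worked case, xviii in Scenario 1: SE² = (2/422) × 1.21 × 0.64 = 0.00367, so SE = 0.0606. At 0.2, Φ(0.12/0.0606 - 1.96) = Φ(0.02) = 51%. At 0.4, Φ(0.24/0.0606 - 1.96) = Φ(2.00) = 98%.

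Against an 80% pass mark, xviii fails in every scenario at 0.2, passes only in Scenarios 1 and 2 at 0.3, and passes in all five at 0.4. At 0.2, even an outcome asked of all respondents passes in Scenarios 1 and 2 and fails in 3 to 5.

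**Precision of the estimate that would be lost (xviii, Scenario 1).** By-arm half-width = 1.96 × 0.0606 = 0.119 SD. Multiplied by √(p(1 - p)), this is 3.6 points at p = 0.1 and 5.9 at p = 0.5 (base rates assumed). Section 7 frames xii-xviii as the effect of attending, so divide by 0.6: about 5.9 to 9.9 points. If baseline data explain nothing (r = 0), SE = √(0.00474 × 1.21) = 0.0757 and the half-width for the effect of attending is about 7.4 to 12.4 points. Uncertainty in the attendance rate is ignored.

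**The case against.** The strongest reply is that the check is not as open as it looks. Section 10 describes its software, power, significance level, ICC and autocorrelation in general terms, several of them for all outcomes. The input that section 7 usually names as missing is a base rate or mean. The natural reading is the section 10 calculation rerun once that input is known. This stands: a reader might infer that the calculation is wholly undefined, and the documents do not support that. What they leave open is the target effect, the timing and the consequence of failure.

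A reader might also infer that outcomes will be selected on their results. Power computed at the observed effect would do that: reaching 80% needs z of 1.96 + 0.84 = 2.80, or p of about 0.005. The plan nowhere says that observed effects enter, and the base-rate rationale points to a fixed target. Under a fixed target the harm is missing estimates, not materially biased ones.

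Two apparent contradictions are weaker than they seem. The outcome ii text can be read as nested: estimate it if power allows, at 10% first, then at 20% and 30% if power also allows. The mismatch with section 3.2 is thin: exercise appears without a power condition under H4a and H5a, but the overlap of xx-xxi with H3a rests on the softer wording. Nor does the remark in section 10.2 that attenders are not compared between arms settle how the monitoring data will be used, since it answers a concern about shared facilities.

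Finally, the conditions are declared in advance, so a reader could see which outcomes were dropped, and for SF-36 and labour the plan already expects no detectable effect. This lowers the severity but does not restore the missing estimates.

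**Conclusion.** The point holds in a limited form. Followed as written, section 7 can withhold randomised estimates for 14 or 15 of 29 items, depending on how outcome ii is read, and these include outcome ii and the advice outcomes. For xviii, reporting would turn on an unstated target, because power moves from 38-55% to 91-99% as the target goes from 0.2 to 0.4. In Scenario 1 the withheld estimate would be imprecise but informative, with a half-width of about 5.9-9.9 points for the effect of attending (7.4-12.4 without help from baseline data).

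These figures assume an 80% pass mark carried over from section 10, a 31% overweight share and base rates of 10-50%. Outcomes i and iii-xi are not conditional, so any inference that the principal result is at risk is unsupported. Severity is minor to moderate: a cheap improvement.

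**What to change.** Delete the ex-post power conditions in section 7. State that every listed outcome, including outcome ii at the 10%, 20% and 30% thresholds, is estimated and reported with its 95% CI, with counts by arm where events are too sparse to model. Label the outcomes now conditional as secondary or exploratory. This also settles the reading of outcome ii and the mismatch over exercise.

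If a statement of sensitivity is wanted, print a detectable effect beside each estimate, computed without using arm. Take the inputs from pooled baseline data where the item exists at baseline, and use the smaller denominators for xii-xiv and xviii. Fixing a target in advance and computing power from pooled baseline data would remove the ambiguity for those items, but outcomes that fell short would still go unestimated.

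The cost is protocol wording and a few more rows in the results tables, some with wide intervals.

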10.1 Parameter values

To the extent that it is possible given the estimates available, we have strived to base the choice of parameter values on evidence. However, it must be acknowledged that, as is often the case with power calculations, the evidence is often lacking or meagre, and we often must resort to guesstimates. In doing so, we have endeavoured to err on the side of conservatism and have conducted sensitivity analyses.

Power

Power is set to 80% and statistical significance to 5%.

Minimum detectable effect size

We calculate the sample size necessary to detect a small effect size (δ) defined as 0.2 standard deviation (SD) units (Cohen 1992). Consider our main outcome i) – the 10-year risk of a heart attack or stroke predicted by the office-based Globorisk algorithim. Given an estimated mean 10-year CVD risk of 11.35% in the control group, which we obtain from Globorisk for individuals aged 40-69 with mean values of all risk factors, if the standard deviation is one fifth of the mean, then an effect size of 0.2 SD corresponds to a 4% reduction in the mean. The assumption that the standard deviation is one fifth of the mean is based on estimates of the distribution of 10-year CVD risk scores (Gale et al 2014; Gray et al 2014). However, we caution that these estimates are not obtained using the Globorisk algorithm and most are for samples of high-income country populations.⁷

We deliberately choose a small effect size in order to ensure that our samples will be sufficient to detect only marginal impacts of the interventions on the risk factors that determine the CVD risk prediction. The logic is threefold. First, risk factors such as smoking and weight are notoriously hard to influence. Second, our information intervention is of unknown effectiveness and we recognize a possibility that a non-negligible fraction of respondents are unable to absorb the information provided on their CVD risks. Third, while the procedures defined by the PhilPEN protocol are proven to be effective, our aim is to establish effectiveness as the program is implemented, which may fall well short of the stipulated testing, medication and counselling.

For mean systolic blood pressure (outcome iii), mean BMI (v) and mean waist circumference (viii), we obtain the estimated control group means from measures taken in the 2013 National Nutrition Survey (NNS) for individuals aged 40-69 (FNRI-DOST, 2015). The standard deviation is assumed to be one seventh of the mean for systolic blood pressure, one fifth of the mean for BMI and one ninth of the mean for waist circumference based on Ezzati et al (2004). In each case, we set the minimal detectable effect size to 0.2 SD units of the mean.

Control group proportions for elevated blood pressure (outcome iv), overweight/obese (vi), smoking (vii), central adiposity (ix), undiagnosed hypertension (x) and hypertension medication (xi) are also taken from the 2013 NNS for individuals aged 40-69. For these binary outcomes, we set the minimal detectable effect size to the small value defined by Cohen (1992) as 0.2 of his h-index.

Intra cluster correlation

⁷ Using the Framingham algorithm for 10-year CVD risk (D'Agostino et al 2008), Gale et al (2014) report a mean of 14.3% and a standard deviation of 2.59 for an English sample of 60+, non-frail persons with no history of CVD. A small study of 40+ employees without previous CVD in a region of Wales reports means (standard deviations) of non-laboratory based Framingham 10-year CVD risk of 10.7% (2.4) for males and 4.8% (1.2) for females (Gray et al 2014).

To the best of our knowledge, there are no estimates available of the intra cluster correlation for (predicted) 10-year CVD risk with clusters defined by communities resembling the size of Filipino barangays. Some idea of the correlation is given by ICCs for CVD risk factors, which determine predicted risk. Table 3 provides estimates of such ICCs for clusters defined at the level of primary care practice obtained from three North American studies.

While homogeneity of CVD risk factors within Filipino barangays need not necessarily closely resemble the homogeneity observed within primary care practices in North America, these estimates at least give an idea of the ICC that might be expected. We set the ICC at 0.1, which is almost twice the highest estimate for any risk factor in Table 3. This is even more conservative than might appear at first sight since one would expect there to be even less within community homogeneity in CVD risk predicted on the basis of all risk factors than there is in each individual risk factor individually.

Table 3 Estimates of intra cluster correlation coefficients for CVD risk factors at the level of primary care practices in North America

	Eastern Ontario	Rhode Island and Massachusetts	Vermont				
	Singh et al (2015)	Parker et al (2005)	Littenberg & MacLean $(2006)^{\pm}$				
Systolic Blood Pressure	0.054	0.047	0.042				
Low Density Lipoprotein	0.035	0.006	0.045				
Fasting Blood Glucose	0.023	0.016	N/A				
Body Mass Index	N/A	0.031	0.011				
Smoking	N/A	0.036	0.005				

 \pm Individuals with diabetes only.

For all other outcomes, we also assume an ICC of 0.1 in our baseline power calculations and test sensitivity to revising the value downward to 0.05.

Cluster size

We aim to observe 10 individuals within each cluster at follow-up who have been exposed to an intervention (or are in the control group). To achieve this, we sample a larger number at baseline to allow for attrition and non-eligibility for the lottery intervention. This cluster size is set to achieve a balance between constraining the sample size while limiting costs incurred by surveying in many barangays.

Autocorrelation in outcomes

We will estimate treatment effects using ANCOVA. That is, the post-treatment outcome observed at follow-up will be regressed on an indicator of treatment group membership and the pre-treatment outcome, plus covariates observed at baseline. The coefficient on the treatment indicator is the estimated treatment effect. For given power and minimal detectable effect size, the required sample size is decreasing with the autocorrelation of the outcome (as well as the proportion of its variance that can be explained using baseline values of covariates).

Estimates of the autocorrelation in predicted 10-year CVD risk are not available, as far as we are aware. Age, sex, smoking and BMI, four of the five predictors of CVD risk used by Globorisk, are obviously very highly autocorrelated. The fifth predictor -a single visit measure of blood pressure -can be

expected to display much lower serial correlation. Blood pressure can vary depending on recent activity and diet, although we will follow a standard protocol for its measurement. It may also vary with the enumerator, although this will be minimized by use of an electronic meter and we can control for enumerator effects.

In addition to the baseline value of the outcome, we will also control for a very larger battery of baseline covariates, including socioeconomic characteristics, medical history, health behavior and knowledge of risk factors.

Admittedly, we do not have a good idea of how the follow-up outcome will vary with all of these factors. We assume for the main power calculations a correlation of 0.6, which corresponds to an explained variance of 0.36. This would seem to err on the side of conservatism, given the very extensive set of covariates that can be used. We use the same value for all outcomes. We test sensitivity of the required sample size to reducing the autocorrelation to 0.4.

Attrition rate

We assume an attrition rate of 10%. This seems reasonably conservative given that the follow-up survey will be only 6-7 months after the baseline and we will make efforts to track respondents in the interim period. This will consist of obtaining the cellphone/ contact numbers of all respondents during the baseline interview. We shall instruct our survey contractor to develop and execute a plan to trace the respondents in between surveys. Their tracing strategy must include contacting each respondent at least once, and possibly twice, during the interim period to check if the respondents are still in the same location. Contact will be through a SMS, a telephone call and, if necessary, a personal visit. We will also engage a local field coordinator (other than the survey firm) to help out in validating the tracing reports of the survey firm, and in coordinating with Barangay Health Worker (BHW) or barangay captain about the whereabouts of respondents that we cannot locate.

Adjustment for refusal, ineligibility and item non-response

Individuals who report a diagnosis of heart disease, heart attack, stroke or diabetes, or who are taking medication for hypertension or diabetes will be ineligible. We must first screen the initially sampled individuals to identify these cases. Using data from the NNS, we estimate this group will amount to 14% of those initially sampled. Other sampled individuals will be eligible but will refuse to give consent to participate. We assume 15% of those sampled will not give their consent. Costs will be incurred performing the initial screening of sampled households before the ineligible and non-consenting cases are identified. We adjust the initially selected sample upwards to allow for these non-usable respondents. A similar adjustment is made for an assumed 5% of the eligible sample who will not answer all requisite questions or complete all measurements despite initially giving consent.

Compliance rate

Not all respondents who are offered a voucher will go to a RHU/CHC for a checkup and so get the lottery ticket to which they are entitled. And some of the control group will go to the RHU/CHC despite not being offered any inducement. We have no firm evidence on which to hazard a guess about the extent to which the offer of a lottery ticket will be effective in persuading people to go for a checkup. Based on the facts that the offered prize of P5000 (US\$100) is roughly equivalent to 14 days' earnings at the average wage in the province, and from discussions with health workers in the area, we believe that response will be high. We assume a compliance rate of 60% and conduct sensitivity analysis setting this as low as 50%.

Table 4 summarises all the parameter values used in the various scenarios considered in the power calculations.

Parameters	Scenario 1 (main)	Scenario 2	Scenario 3	Scenario 4	Scenario 5
Significance level (α)	0.05	0.05	0.05	0.05	0.05
Power $(1-\beta)$	0.8	0.8	0.8	0.8	0.8
Minimum detectable	0.2	0.2	0.2	0.2	0.2
standardized effect size (δ)					
Attrition rate	0.1	0.1	0.1	0.1	0.1
Refusal to consent rate	0.15	0.15	0.15	0.15	0.15
Item non-response rate	0.05	0.05	0.05	0.05	0.05
Ineligibility rate	0.14	0.14	0.14	0.14	0.14
Average cluster size at follow-up	10	10	10	10	10
Intra-cluster correlation	0.1	0.05	0.1	0.05	0.1

Table 4 Parameter values used in power calculations

Autocorrelation in outcomes	0.6	0.6	0.6	0.6	0.4	
Compliance rate in lottery intervention	0.6	0.6	0.5	0.5	0.6	

	Control group	Treatment group	
Mean CVD risk	11.35	10.89	
Mean systolic BP in mm Hg	125.61	122.02	
Proportion with BP \geq 140 mm Hg	0.31	0.22	
Proportion on BP medication	0.10	0.16	
Proportion of undiagnosed hyper-tension	0.20	0.13	
Mean BMI	23.35	22.41	
Proportion with BMI > 25	0.31	0.22	
Mean waist circumference in cm	82.01	80.19	
Proportion with high waist circumference	0.40	0.30	
Proportion currently smoking	0.17	0.10	

Table 5 Means of outcome variables used in power calculations

